Despite the overall improvement in posterior eye OCT shape in this pilot study, there remained a bias between the OCT measures and MRI. The possible sources of error in this preliminary work (other than small

sample size) include the lower resolution of these non-orbital MRI scans, the use of schematic model anterior eyes, motion errors, and the unknown system-to-cornea distance to control for scan magnification.

In this proposal, we will perform a prospective study with dedicated orbital MRIs, with measured and model-free determination of all ocular surfaces, with decreased patient motion from the faster SSOCT system, and with direct measurement of the system-to-cornea distance (see SA1.Research Design.System Calibration). With these improvements, we anticipate that we will decrease the curvature difference between MRI and OCT to less than a millimeter (resolution of our MRI). Further, we will compare surface topographies of myopic patients with known morphometric changes (e.g. staphylomas) imaged with MRI and OCT.

SA3. Research Design. Algorithm development and validation. We will extend our previously developed three-dimensional refraction correction algorithms [20] to perform ray tracing of the OCT scan paths through the ocular surfaces contained within the whole eye OCT images. The anterior eye image content will be segmented and corrected of optical distortions as in Aim 2 (refraction, non-telecentricity, motion). Group refractive indices for our light source ($\lambda_0 = 1060$ nm) will be used for refraction correction as described in detail in SA2.Research Design.Algorithm Development. For the lens, we will measure the group index for IOLs, and use a polynomial model for natural lenses [52] as was used in our pilot work [4]. The retinal layers of the posterior eye will also be segmented in preparation for post-processing [53]. With a known system topology, measured and hence known system-to-cornea distance per patient, and an accurate representation of the anterior eye components, we will determine the spatial orientation of the OCT scan paths to the posterior eye. With these OCT scan paths, the posterior eye A-scans will be properly repositioned spatially to restore anatomic accuracy.

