Each enrolled subject will undergo the following imaging: optical biometry (LenStar, Haag-Streit), whole eye OCT, and MRI imaging. MRI will be performed on the clinical research scanners at the Duke Brain Imaging and Analysis Center (see support letter from director [name]). Annually, with the assistance of dedicated research coordinators, they image over 2000 subjects with MRI for over 70 research projects. Their scanner (GE) has a magnetic field strength of 3.0 Tesla. A high resolution T1 FSPGR sequence will be used to acquire images of the subject's eyes. Images will be acquired in the axial plane, with FOV=25.6cm, TR=8ms, TE=3ms, flip angle=12, 512x512x50 imaging matrix, completely covering the eyes. A second T2 weighted sequence will be acquired at the same slice prescription with TR=3s and TE=25ms. With these scan parameters, each voxel will be 0.5 mm^3 . During scanning, a fixation target will be provided to minimize eye motion during acquisition.

[figure not shown]

FIGURE 10. General overview of clinical study design to determine the difference between OCT and MRI posterior eye images. Using radius of curvature as a general measure of shape, we will compare the paired differences between the two modalities. In a second study in subjects with staphylomas, we will use root mean square difference to describe the topographic differences between the two registered modalities.

The radius of curvature of the posterior eye will be measured via surface fitting of the posterior eye data from OCT and MRI. To have 80% power to detect a 0.5 mm difference in radius of curvature between OCT and MRI using a paired one-sample t-test, we will need to enroll a minimum of 48 normal pseudophakic subjects (PROC POWER, SAS v9.3). This power calculation assumes that with our whole eye OCT and improved algorithms, we will halve the standard deviation of the difference between MRI and OCT found in our initial study (2.3 mm), resulting in an estimated standard deviation of 1.2 mm. At a 0.5 mm difference, we will be at the effective voxel resolution of the MRI scans and should also have more than enough resolution to identify the large-scale topographic abnormalities noted in previous MRI studies of myopia [25,26].

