While the natural lens does present an ambiguity, by first imaging pseudophakic subjects in group 1 and part of group 2, we will first refine and validate our algorithms independent of the natural lens. This lays the foundation for subsequently investigating and isolating any differences between MRI and OCT resulting from imaging phakic subjects in group 2. Our preliminary algorithm using a polynomial gradient index lens model [52] demonstrated reduced differences between OCT and MRI [4]. Alternate OCT based natural lens models [55] can be incorporated into our reconstructions for reanalysis of captured and stored image data if necessary. Our use of these gradient indices is far more sophisticated than the average refractive indices successfully used for ocular axial biometry both in research and clinically [56,57 and commercially available partial coherence interferometers]. If necessary, we can similarly use average indices. Importantly, with the validated pseudophakic group, we will be able to compare and contrast quantitative performance of OCT in phakic subjects. This data has important implications for both the OCT and myopia communities.

Timetable. We anticipate this ambitious project will require the full requested five year project period to complete. We anticipate the whole eye SSOCT system design and assembly will take approximately one year. Algorithm development will begin with initial images of phantoms and normals and can occur concurrently with clinical imaging because all acquired images can be post-processed at a later date if necessary. Data collection, data analysis, and publication will occur on a rolling basis throughout the project.

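### Aim 3 refines its reconstruction algorithms on Group 1, the 48-subject sample for the OCT-MRI test, without fixing which version is tested or masking refinement to MRI

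*Combined protocol and SAP*

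**What the plan says.** The Group 1 part of the Aim 3 clinical study compares posterior-eye radius of curvature from OCT and MRI in the same eyes with a paired t-test. For 80% power at a 0.5 mm difference, "we will need to enroll a minimum of 48 normal pseudophakic subjects". The planning standard deviation is 1.2 mm, about half the pilot's 2.3 mm, on the assumption that the new system and improved algorithms will achieve that reduction.

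SA3. Potential Problems & Alternative Strategies gives the same subjects a second role: "by first imaging pseudophakic subjects in group 1 and part of group 2, we will first refine and validate our algorithms". The sentence goes on to say that this is done independently of the natural lens, which explains why pseudophakic eyes come first. Later in that paragraph Group 1 has become a reference: "with the validated pseudophakic group, we will be able to compare and contrast quantitative performance of OCT in phakic subjects".

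On timing, the Group 2 text places that group after Group 1 has been enrolled and analysed. The Timetable says that algorithm development will start with phantoms and normals and "can occur concurrently with clinical imaging because all acquired images can be post-processed at a later date if necessary". It adds: "Data collection, data analysis, and publication will occur on a rolling basis throughout the project".

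Validation outside the patient sample consists of a model eye whose recovered curvature is compared with the manufacturer's value (SA3. Research Design). SA3. Expected Outcomes lists phantom validation separately from the MRI comparison. No section states an algorithm freeze, a version lock, masking of developers to MRI, or a separate set of human eyes for developing the posterior reconstruction.

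**The concern.** An algorithm tested on the eyes used to refine it can look better than it is if the refinement was steered by the test's own outcome. Here that outcome is the OCT-MRI difference. MRI is the only in-vivo reference for posterior shape that Aim 3 names, and the pilot algorithm was credited because it "demonstrated reduced differences between OCT and MRI". The team also expects the new work to shrink the difference that remained in the pilot. MRI agreement is therefore a natural guide for refinement unless the plan rules it out.

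The direction of the error matters. Aim 3 sets out to show that corrected OCT is comparable to MRI and to provide a basis for replacing it. Refinement guided by the Group 1 differences would pull the reported mean difference towards zero and make a real bias harder to detect. Both effects favour that conclusion. If refinement never sees MRI, this loss does not arise, but as the plan stands a reader could not tell which happened.

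**Working it through.** **1. The plan's own figure.** Inputs from SA3. Research Design, Group 1: difference 0.5 mm, SD of the paired difference 1.2 mm, 80% power, paired one-sample t-test. Aim 3 states no alpha or sidedness. I assume two-sided 0.05; alpha 0.05 is stated only for Aim 2.

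- Noncentrality = (0.5 / 1.2) × √48 = 2.887; critical t on 47 degrees of freedom = 2.012.
- Noncentral-t power: 80.7% at n = 48 and 79.9% at n = 47.

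The minimum of 48 reproduces exactly, so the sample size is not in question. The power applies to one algorithm fixed without reference to the Group 1 differences.

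**2. The sequence, read side by side.**

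| Section | What it fixes | What it leaves open |
|---|---|---|
| SA3. Research Design, Group 1 | Sample, endpoint, test | Which algorithm version is tested |
| SA3. Research Design, Group 2 | Group 1 is analysed before Group 2 | Whether Group 1 is re-run later |
| SA3. Potential Problems | Refinement uses Group 1 and part of Group 2 | Whether refinement sees MRI |
| Timetable | Development may overlap imaging; stored images may be re-processed; analysis is rolling | When development stops |

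If Group 1 is analysed first and refinement extends into Group 2, some refinement comes after the Group 1 differences are known. It affects the Group 1 result only if Group 1 is re-processed, which the Timetable permits. The plan does not say whether the reported result comes from the version before or after that refinement.

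**3. Illustration of the effect.** The number of versions, their biases and the correlation of their errors are assumptions; none is in the documents. Set-up: n = 48, SD 1.2 mm, 20,000 simulated trials, and per-eye error correlation between versions of 0.5, 0.8 or 0.9. The version with the smallest absolute mean OCT-MRI difference is selected and then tested on the same 48 eyes. Ranges run across the three correlations.

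| Versions, all with true bias 0.5 mm | Bias detected | Mean reported bias |
|---|---|---|
| One, frozen | 81% | 0.50 mm |
| Best of two | 70-76% | 0.43-0.47 mm |
| Best of three | 63-73% | 0.40-0.45 mm |

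When the versions truly differ, part of the fall in reported bias is real improvement. The distortion is then the gap between the reported bias and the selected version's true bias:

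| True biases of three versions | Correlation | Reported | True bias of selected version |
|---|---|---|---|
| 0.6 / 0.5 / 0.4 mm | 0.5 | 0.37 mm | 0.44 mm |
| 0.6 / 0.5 / 0.4 mm | 0.8 | 0.39 mm | 0.42 mm |
| 0.6 / 0.5 / 0.4 mm | 0.9 | 0.40 mm | 0.41 mm |
| 0.7 / 0.5 / 0.3 mm | 0.5 | 0.30 mm | 0.33 mm |
| 0.7 / 0.5 / 0.3 mm | 0.8 | 0.30 mm | 0.31 mm |
| 0.7 / 0.5 / 0.3 mm | 0.9 | 0.30 mm | 0.30 mm |

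So the effect runs from almost nothing, when versions differ clearly and their errors are highly correlated, to a loss of up to 18 percentage points in detection (81% to 63%) in the cases shown.

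**The case against.** The strongest reply is that the concern rests on one word, refine, in a sentence about taking the natural lens out of the problem. SA1. Potential Problems & Alternative Strategies describes the same step as validation only. The method also offers little to tune. It is ray tracing with calibrated pixel pitch and system-to-eye distance, measured group indices, imaged surfaces and manufacturer lens prescriptions, backed by the model-eye check. No parameter fitted to MRI appears anywhere, and no competing versions for Group 1 are named. The pilot was evaluated against MRI, which is not the same as being tuned to it. Its remaining bias was reported openly and put down to physical causes, for which the planned remedies are mainly better measurements.

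All of this stands as a limit on the likely size. It does not settle choices made on human eyes, such as segmentation, motion handling and surface fitting. Nor does it say which version is tested.

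Two stronger readings are tempting. A reader might infer that the plan will calibrate OCT to MRI. No passage says so, and the extreme case in which an offset is fully matched to MRI and detection falls to zero is not proposed anywhere. A reader might also cite the sentence "Alternate OCT based natural lens models [55] can be incorporated into our reconstructions for reanalysis of captured and stored image data if necessary" as evidence of competing versions. It concerns natural lenses, for which the plan already intends to "use a polynomial model for natural lenses [52] as was used in our pilot work". Group 1 is entirely pseudophakic, so that sentence is no evidence about the 48-subject test.

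Finally, treating a non-significant difference as proof of agreement is a separate weakness that would exist with a frozen algorithm. The present point does not depend on it, because the reported mean difference would itself be understated.

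**Conclusion.** The concern holds as a missing safeguard. The plan uses Group 1 both to refine the algorithms and to test them against MRI, and neither a freeze nor masking keeps the two apart. Whether harm follows depends on whether refinement is guided by the Group 1 OCT-MRI differences, which the documents neither state nor exclude. If it is, a real bias is understated and less often detected. The documents do not allow that amount to be estimated, and the simulated figures show direction and possible scale only. They rest on two-sided alpha 0.05, SD 1.2 mm, a small number of assumed versions and selection by smallest mean difference. The minimum of 48 is correct on its stated inputs. The change is worth making because it is cheap and protects the main comparison of Aim 3. Confidence is medium, given how little scope for tuning the method describes.

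**What to change.** Add a short paragraph to SA3. Research Design stating that:

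- refinement uses phantoms, the model eye and OCT images, including Group 1 OCT images, by staff masked to the MRI radii;
- the pipeline version and surface-fit settings are recorded and frozen before any Group 1 MRI radius is linked to its OCT result;
- that version is run once on all 48 subjects for the primary paired comparison;
- any later re-run of Group 1, including one prompted by work in Group 2, is labelled exploratory.

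The cost is a few sentences, version control and masking of the MRI radii. The sample of 48 and the stated 80% power are unchanged, because no subject is withdrawn from the test. The downside is that improvements learned from MRI cannot enter the primary Group 1 result. Masking is also cheaper than holding out eyes. For example, reserving 10 of the 48 for MRI-linked tuning would leave 38 for the test, with noncentrality (0.5 / 1.2) × √38 = 2.569 and power of 71%. Keeping 48 for the test would then mean enrolling 58.
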